1.0 Introduction

Lead durability and integrity depend on several factors, such as lead design, lead material, and mechanical stress. More than half of all lead complications are insulation defects, most frequently due to subclavian crush syndrome, abrasion of the lead by direct contact to the pulse generator (i.e. pacemaker, ICD, or CRT-D), or abrasion of the lead against adjacent leads. Often these present clinically with evidence of impedance changes or inappropriate ventricular sensing and defibrillation¹.

St. Jude Medical Riata® and Riata® ST family of leads are high voltage implantable cardioverter defibrillator (ICD) endocardial leads with Silicone insulation. QuickSite® and QuickFlex® left ventricular leads also utilize silicone rubber for insulation. Silicone rubber, while representing the industry's most commonly used defibrillation lead insulation material over the past 20 years, has been observed to be vulnerable to abrasion^{2,3,4}. Abrasion of silicone defibrillation leads is acknowledged within the clinical community as a well known clinical risk and is well documented in the literature as the number one cause of lead failure across the industry with reported failure rates ranging from 3 to 10 %^{5,6,7}.

A more recently reported manifestation of Riata lead insulation and QuickSite/QuickFlex lead abrasion involves conductors that are outside the lead body as detected by x-ray, fluoroscopy, or post-explant physical examination. This phenomenon, known as inside-out abrasion with externalized conductors, occurs when internal abrasion processes produce an outer insulation breach significant enough to allow the conductor to separate from the lead body in isolated regions. Such a separation does not guarantee an electrical abnormality because the conductors themselves are insulated with a robust layer of ethylenetetrafluoroethylene (ETFE) polymer.

The prevalence of externalized conductors proximal to the RV coil in Riata/Riata ST leads has been reported to vary from 0.5% to 33.3% depending on the lead model⁸⁻¹¹. Some of these cases of externalized conductors have been accompanied with inappropriate shocks, oversensing, increased pacing impedance/ threshold and lead noise. It remains unclear whether externalized conductors caused these electrical problems, as approximately 85% of the returned leads with externalized conductors do not have their ETFE insulation compromised and therefore should not be the cause of any reported electrical problem.

The Durata® family of ICD leads utilizes a silicone polyurethane co-polymer insulation known as Optim which has been associated with a significant reduction in abrasion when compared to Riata and Riata ST silicone insulated leads. Although the incidence of these insulation abrasion issues is extremely low in Durata leads, the Durata leads are being included in this study for comprehensive

analysis across all St. Jude Medical ICD lead types. This study aims to prospectively determine the prevalence and incidence of lead compromise evidenced by imaging (includes externalized conductors and other visual lead anomalies, by each subcategory, as listed in Appendix A) and electrical dysfunction in patients with Riata, Riata ST silicone ICD, QuickSite/QuickFlex CRT and Durata ICD leads. Prevalence as well as incidence of externalized conductors and other visual lead anomalies will be separately analyzed and reported. In addition, this study will provide information to the physicians regarding the possibility that an observation of externalized conductors with normal electrical function may progress to an electrical malfunction. The SJM Cardiac Lead Assessment Study is sponsored by St. Jude Medical (SJM) and constitutes the modification of the “Riata Lead Evaluation Study”.

2.0 Purpose

The objectives of the study are:

1. To determine the prevalence of externalized conductors at enrollment in Riata®, Riata® ST Silicone, QuickSite®/QuickFlex® and Durata® leads
2. To determine the prevalence of other visual lead anomalies by each subcategory per Appendix A at enrollment in Riata®, Riata® ST Silicone, QuickSite®/QuickFlex® and Durata® leads
3. To determine the prevalence of electrical dysfunction[§] at enrollment in Riata®, Riata® ST Silicone, QuickSite®/QuickFlex® and Durata® leads
4. To determine the incidence of externalized conductors after enrollment in Riata®, Riata® ST Silicone, QuickSite®/QuickFlex® and Durata® leads
5. To determine the incidence of other visual lead anomalies by each subcategory per Appendix A after enrollment in Riata®, Riata® ST Silicone, QuickSite®/QuickFlex® and Durata® leads
6. To determine the incidence of electrical dysfunction[§] after enrollment in Riata®, Riata® ST Silicone, QuickSite®/QuickFlex® and Durata® leads.
7. To evaluate the 30-day adverse event rate associated with lead revision procedures (include lead extractions or abandonments with or without lead replacement) in Riata®, Riata® ST Silicone, QuickSite®/QuickFlex®, and Durata® families of leads
8. To determine the prevalence of “other insulation anomalies” in “returned leads” for Riata®, Riata® ST Silicone, QuickSite®/QuickFlex®, and Durata® families of leads. “Other insulation anomalies” include any of the following:
 - Internal abrasion short under RV shock coil
 - Internal abrasion short under SVC shock coil
 - Exposed conductors defined as a breach of the outer insulation
 - Breach of the internal silicone lumen tubing, but the conductor cable is contained within the lead body diameter.

[§]”Electrical dysfunction” is determined to be present after adjudication of the following cases of potential electrical failures that led to the lead being either

surgically capped/extracted or electrically abandoned. Potential electrical failures include the following:

- Presence of non-physiologic noise not due to external interference
- Rise in pace/sense (p/s) conductor impedance to $> 2000 \Omega$ or increase of more than 200Ω over previous 6 months or increase of 400Ω over any period of time
- Decrease of more than 200Ω over previous 6 months or to impedance $< 200 \Omega$ from baseline impedance $> 300 \Omega$ or decrease of 400Ω over any period of time
- Change in any high voltage coil impedance of $> 25 \Omega$ or to $> 125 \Omega$ or $< 20 \Omega$
- Capture threshold $> 5 \text{ V}$ or an increase of $\geq 2 \text{ V}$ from baseline (all measurements) of $< 1 \text{ V}$

NOTE: In all cases, external sources of "noise" and other header-connector causes would be excluded. Functional abnormalities, including exit block and physiologic oversensing in the presence of an electrically intact lead are not electrical failures.

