3.2 Study Outcome Measures

3.2.1 Primary Outcome Measures

3.2.1.1 The prevalence of electrical dysfunction in the Riata, Riata ST, QuickSite/QuickFlex (1056T, 1058T, 1156T, 1158) and Durata leads.

Lead Population

All enrolled leads within the Riata, Riata ST, QuickSite/QuickFlex (1056T, 1058T, 1156T, 1158) and Durata lead groups.

Analysis:

The prevalence of electrical dysfunction will be calculated as the number of leads that have electrical dysfunction at the time of enrollment in each of the 4 lead groups divided by total number of leads in enrolled patients in each of the 4 lead groups. The one-sided 95% UCB for prevalence will be calculated using Clopper-Pearson exact method.

3.2.1.2 The prevalence of externalized conductors in the Riata, Riata ST, QuickSite/QuickFlex (1056T, 1058T, 1156T, 1158) and Durata leads.

Lead Population

All enrolled leads within the Riata, Riata ST, QuickSite/QuickFlex (1056T, 1058T, 1156T, 1158) and Durata lead groups.

Analysis:

The prevalence of externalized conductors will be calculated as the number of leads that have been shown to have externalized conductors by imaging at the time of enrollment in each of the 4 lead groups divided by total number of leads in enrolled patients in each of the 4 lead groups. The one-sided 95% UCB for prevalence will be calculated using Clopper-Pearson exact method.

3.2.1.3 The prevalence of other visual lead anomalies by each subcategory (fracture, kink, subclavian crush, other irregularities) in the Riata, Riata ST, QuickSite/QuickFlex (1056T, 1058T, 1156T, 1158) and Durata leads.

Lead Population

All enrolled leads within the Riata, Riata ST, QuickSite/QuickFlex (1056T, 1058T, 1156T, 1158) and Durata lead groups.

Analysis:

The prevalence of other visual lead anomalies (by each subcategory) will be calculated as the number of leads that have been shown to have other visual anomaly (by each subcategory) at the time of enrollment in each of the 4 lead groups divided by total number of leads in enrolled patients in each of the 4 lead groups. The one-sided 95% UCB for prevalence will be calculated using Clopper-Pearson exact method.

3.2.1.4 The annual hazard rate of lead electrical dysfunction (from enrollment) by lead subgroups in the Riata, Riata ST, QuickSite/QuickFlex (1056T, 1058T, 1156T, 1158) and Durata leads.

Lead Population

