8.0 Deaths

All patient deaths that occur during this study must be reported to St. Jude Medical within 10 working days of the center being notified. Notification of death should include a detailed statement of the pertinent events and be signed by the investigator in addition to the appropriate case report forms (Patient Death form, Withdrawal form, and Product Out of Service form). It is the investigator's responsibility to notify the IRB/MEC per the IRB/MEC policy. The CEC will review and classify all patient deaths. Details of death and the following information, if available, should be provided in a letter to St. Jude Medical by the investigator summarizing the patient's course since enrollment in the study:

- Date of death
- Place death occurred (e.g. hospital, nursing home, patients home)
- If death was witnessed
- Identification of the rhythm at the time of death, if known
- Cause of death
- Any other circumstances surrounding the death
- Approximate time interval to death from the initiating event
- Autopsy report (if performed)
- Whether it was device and/or procedure related
- Whether it was related to the study
- Device configuration at the time of death

Provide clinical notes and witness statements. If possible, interrogate the pulse generator. Retrieve and print all episode diagnostics, IEGMs, and programmed parameters. If applicable, the pulse generator should then be programmed OFF.

Every attempt should be made to explant the pulse generator and/or leads intact. Any explanted devices or leads should be returned to St. Jude Medical for analysis promptly. In the event that the device is not explanted, the above procedure must be followed to retrieve the data. The reason the pulse generator and/or lead(s) are not being returned to St. Jude Medical must be stated clearly on the case report form.

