11.3 Electrical Data Adjudication Committee

Electrical Data Adjudication Committee (EDAC) will be comprised of at least three Electrophysiologists or Cardiologists experienced in analyzing and interpreting device data. The role of the EDAC is to adjudicate the device session records to determine the presence of electrical dysfunction in the SJM Cardiac Lead Assessment study patient population. Committee members will be reviewing device session records for all leads taken out of service during the course of the study. Data will be sent either electronically or in a paper binder to the committee members. Once the adjudication is complete, an electrical data adjudication form will be collected per patient.

Only the adjudicated cases of electrical dysfunction will be included in the post market surveillance reports. Percentage of leads with electrical dysfunction (based on the definition in section 2.0) will be part of the reports.

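### Read literally, electrical dysfunction excludes a failure in a lead still in service when the patient dies, so the hazard in 3.2.1.4 can be biased downward

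*Combined protocol and SAP*

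**What the plan says.** Section 2.0 makes electrical dysfunction depend on "adjudication of the following cases of potential electrical failures that led to the lead being either" "surgically capped/extracted or electrically abandoned". It then lists the qualifying electrical findings: noise, impedance changes and capture threshold changes. Section 3.2.1 makes "The annual hazard rate of lead electrical dysfunction (from enrollment) by lead subgroups" a primary outcome, and 3.2.2.3 to 3.2.2.5 add Kaplan-Meier curves that end in the same event.

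Section 8.0 requires three forms at each death ("Patient Death form, Withdrawal form, and Product Out of Service form"). It also asks for device interrogation, stored episodes and electrograms, and for an attempt to recover the leads. On classification it says: "The CEC will review and classify all patient deaths".

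Section 11.3 sets the EDAC's scope: "Committee members will be reviewing device session records for all leads taken out of service during the course of the study". It limits reports to adjudicated cases and refers back to section 2.0: "Percentage of leads with electrical dysfunction (based on the definition in section 2.0) will be part of the reports".

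**The concern.** The definition has two parts: an electrical finding, and a lead action that the finding brought about. A patient who dies with a failed lead in place can satisfy the first part but has no opportunity to satisfy the second. The same failure in a patient who survived to revision would be counted.

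The study runs under an FDA 522 order, and 3.2.1.4 is its main answer on lead malfunction. Leaving out failures found at death can only lower the reported hazard, which is the wrong direction for a safety study. The proportional effect is largest where few events are counted. The concern is with incidence after enrollment and does not affect prevalence at enrollment.

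**Working it through.** **1. Does the text let such a case count?**
- Section 2.0 requires the failure to have led to capping, extraction or electrical abandonment. The list is closed and causal.
- Section 8.0 asks that the generator be switched off after death where applicable, and that leads be explanted. Both steps follow from the death and not from the failure, so neither meets the causal test.
- The Product Out of Service form (8.0) and the EDAC's remit over all leads out of service (11.3) appear to put the records before the EDAC. That settles who reviews the case, not whether it counts. Section 11.3 returns to the 2.0 definition for what is reported.
- Nothing connects the CEC's classification of a death to the electrical endpoint.

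**2. The plan's own mortality figures (section 3.1) reproduce.**
- ICD: 1 - (1 - 0.07)^3 = 19.6%, stated as 20%.
- Left ventricular leads: 1 - (1 - 0.128)^3 = 33.7%, as stated.
- High-voltage mix: 0.6 × 0.20 + 0.4 × 0.337 = 25.5%, as stated.
- Total attrition, high-voltage leads without the Riata allowance: 1 - 0.745 × 0.85 = 36.7%, stated as 37%.

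**3. How many deaths could be involved?** Table 2 targets sum to 560 Riata, 365 Riata ST, 825 Durata and 750 QuickSite/QuickFlex leads. Ignoring competing withdrawal:
- High-voltage: 1,750 × 0.255 = 446.
- QuickSite/QuickFlex: 750 × 0.337 = 253.
- Together about 700. This is an upper figure, because some patients withdraw before they die.

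**4. Durata, allowing for competing withdrawal and assuming constant rates.**
- Death rate: -ln(0.745)/3 = 0.0981 per year.
- Withdrawal rate: -ln(0.85)/3 = 0.0542 per year.
- Observed deaths: 825 × 0.36675 × 0.0981/(0.0981 + 0.0542) = about 195.
- Lead-years, with the stated 37%: k = -ln(0.63)/3 = 0.154, and 825 × 0.37/0.154 = about 1,982.

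**5. Missed events.** The documents do not give the share of deaths with an uncounted lead failure. Assume 0.5% to 2%.
- 0.005 × 195 = 0.98 and 0.02 × 195 = 3.9, so about 1 to 4 events.
- Added hazard: 0.98/1,982 = 0.05 and 3.9/1,982 = 0.20 percentage points per year.

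Share of all failures missed = missed/(missed + counted):

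| Assumed counted hazard | Counted events | Share missed |
|---|---|---|
| 0.5% per year | 9.9 | 0.98/10.9 = 9% to 3.9/13.8 = 28% |
| 2% per year | 39.6 | 0.98/40.6 = 2% to 3.9/43.5 = 9% |

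**The case against.** The strongest reply is that sections 8.0 and 11.3 already send these leads to the EDAC, whose scope is wider than the three listed actions, so the committee might count them. This has some force: the text does not say how the EDAC is to class such a lead, and practice may be more generous than the wording. But a committee that counted the case would be departing from the definition that governs the reports.

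A reader might also infer that every failure ending in death is lost, or that the most serious failures as a class drop out of 3.2.1.4. The documents support neither. A failure that led to capping, extraction or electrical abandonment before a later death is still an event. A patient who dies with a failed lead need not have died of it, so the uncounted cases are not necessarily the gravest.

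Nor do fatal failures go unexamined. The CEC adjudicates deaths and adverse events (11.1). Lead-related adverse events are collected (6.0). A lead returned after death enters primary outcome 3.2.1.7. These routes capture part of the information but do not feed the electrical dysfunction hazard, and 3.2.1.7 covers only insulation anomalies.

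It is also an inference that such a patient leaves the analysis as an event-free exit. Section 3.2.2.3 gives only censoring at 3 years and is silent on death, and section 3.2.1.4 names no estimator. How death is handled is a separate gap.

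Finally, requiring a lead action is a coherent safeguard against sensitive electrical thresholds. Dropping it for every death would count a threshold crossing in a deceased patient that would not count in a living one. That objection stands, and it limits the fix.

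**Conclusion.** The concern holds in a limited form. By its wording, the 2.0 definition leaves out an electrical failure in a lead still in service at death, and 11.3 carries that definition into the reports. The hazard in 3.2.1.4 and the event curves in 3.2.2.3 to 3.2.2.5 can therefore be biased downward. The direction follows from the text; the size does not.

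The Durata range (1-4 missed events; 9-28% of failures at a counted hazard of 0.5% per year, 2-9% at 2% per year) rests on an assumed share of deaths, an assumed hazard, constant rates and target enrollment being met. It also varies the hazard while holding the share of deaths fixed, although the two may move together. It is an illustration, not an estimate. The change is worth making because the committees and the device records it needs are already in the plan.

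**What to change.** - **Sections 2.0 and 11.3:** add as an event an EDAC-confirmed electrical failure in a lead in service at death, when the CEC classes the death as related to the lead or device. Date it at the first electrical evidence.
- **Section 8.0:** have the CEC pass such deaths to the EDAC, together with all available session records from every death. The plan does not list the CEC's categories, so state that relation to the lead or device is one of them.
- **Sensitivity analysis:** repeat 3.2.1.4 and 3.2.2.3 to 3.2.2.5 also counting EDAC-confirmed failures in all other deaths.
- **Reporting:** give, by lead group, the number of deaths without device interrogation and the number classed as device related.

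The cost is a wording change to three sections, more session records for the EDAC to read, and a slightly higher reported hazard. In the sensitivity analysis only, the criterion is looser for deceased than for living patients, and the report should say so. Patient care is unaffected.

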3.0 Clinical Protocol

3.1 Study Design and Scope

This study is a prospective, non-randomized, multi-center, international post market study that will determine the prevalence and incidence of externalized conductors and other visual lead anomalies (as evidenced by imaging) and the risk of progression to electrical dysfunction in a large series of ICD/ CRT-D/CRT-P devices containing one or more of the following SJM leads: Riata leads, Riata ST silicone leads, Durata leads, QuickSite/QuickFlex CRT leads. A patient that has at least one market released lead implanted in time period indicated in Table 1 is eligible for enrollment in the study. Each lead group will be considered separately for independent analysis.

Table 1: Leads Eligible for Enrollment

Lead Group	Model Numbers	Lead Implant Date
Riata	1560, 1561, 1562, 1570, 1571, 1572, 1580, 1581, 1582, 1590, 1591, 1592	2002-2009
Riata ST Silicone	7000, 7001, 7002, 7010, 7011, 7040, 7041, 7042	2006-2009
QuickSite/QuickFlex	1056T, 1058T, 1156T, 1158T	2006-2010
Durata	7120, 7121, 7122, 7130, 7131, 7120Q, 7121Q, 7122Q, 7170Q, 7171Q, 7172Q	2008-2010

In order to determine the prevalence and incidence of externalized conductors, other visual lead anomalies as well as electrical dysfunction in the population of leads being evaluated, a minimum of 1500 leads listed above will be enrolled at up to 60 sites. This will comprise a minimum of 300 leads in the Riata lead group and a minimum of 200 leads in the Riata ST lead group to make a combined total of at least 500 Riata and Riata ST silicone leads. The study will also include at least 500 leads in the QuickSite/QuickFlex and Durata lead groups. All patients will be followed every six months for three years.

Adequate representation across the different ages of the leads is also needed to understand the lead population being studied. Therefore, the leads from each group of leads will be compromised of subgroups based on the age of lead (at enrollment) being studied. The required minimum enrollment for each subgroup per lead group is indicated in Table 2. Even if the minimum enrollments indicated in Table 2 are met, extra enrollments may be required to ensure a minimum of 500 leads in each lead group.

Expected Attrition in patients with high voltage leads

Withdrawals due to death

Assuming an annual mortality of 7% in the ICD patient population, the mortality at 3 years is 20% $[1 - (1-0.07)^3]$ In the recent RHYTHM ICD/QuickSite 1056K left heart lead study, the annual mortality was 12.8%, which would result in a mortality of 33.7% $[1 - (1-0.128)^3]$ at 3 years. If the ICD:CRT-D device mix is 60%:40% then the expected overall mortality in this study at 3 years is 25.5% ($=0.6 \times 0.20 + 0.4 \times 0.337$).

Withdrawals due to reasons other than death

In an ongoing St. Jude Medical post-approval study (SJ4 PAS), the attrition rate due to reasons other than death at 22 months of follow-up is 9%. Thus, it is anticipated that the attrition rate at 3 years for reasons other than death will be 15%.

Assuming that deaths and withdrawals are independent events, the total attrition is expected to be approximately 37% ($= 1 - (1-0.255) \times (1-0.15)$) over 3 years.

Since the Riata/Riata ST leads are recalled, it is more likely that some physicians will explant them, even when electrical function is normal. For this reason, an additional 10% of the patients are expected to be prematurely withdrawn. This leads to a total attrition of approximately 43% ($= 1 - (1-0.255) \times (1-0.15) \times (1-0.10)$) over 3 years.

Expected Attrition in patients with left ventricular leads
Withdrawals due to deaths

In the RHYTHM ICD/QuickSite 1056K left heart lead study, the annual mortality was 12.8%, providing an estimated mortality rate of 33.7 % $[1 - (1-0.128)^3]$ at 3 years.

Withdrawals for reasons other than death

In the ongoing St. Jude Medical post-approval study, the attrition rate due to reasons other than death at 22 months of follow-up is 9%. Thus, it is anticipated that the attrition rate at 3 years for reasons other than death will be 15%.

Assuming that deaths and withdrawals are independent events, the total attrition is expected to be approximately 43.6% ($= 1-(1-0.337) \times (1-0.15)$) over 3 years.

Table 2: Enrollment in Lead Subgroups

Lead Group	Age of Lead at Enrollment (Years)	Min Enrollment	Expected Attrition at 3 years*	Target Enrollment
Riata Silicone	≥ 7	100	47%	195
	≥ 6 and < 7	100	45%	185
	< 6	100	43%	180
Riata ST	≥ 5.5	100	45%	185
	< 5.5	100	43%	180
QuickSite 1056T/1058 and QuickFlex 1156T/1158T	≥ 6	115	46%	225
	≥ 5 and < 6	115	46%	225
	< 5	170	44%	300
Durata	≥ 5	167	37%	275
	≥ 4 and < 5	167	37%	275
	< 4	167	37%	275

*Expected attrition in each of the lead groups is based on the rationale provided above the table as well as larger attrition expected in older leads.

[figure not shown]
At enrollment, medical history, demographic data and lead measurement data will be collected. Additionally, cinefluoroscopy (AP, LAO 45° or the best possible LAO view, RAO 45° or the best possible RAO view) will be performed to determine the prevalence of lead compromise. A copy of

cinefluoroscopy performed as part of separate screening can be used to determine the prevalence of lead compromise as long as all three views (AP, LAO 45° or the best possible LAO view, RAO 45° or the best possible RAO view) are available. In patients with evidence of externalized conductors or other visual lead anomalies (fracture, subclavian crush, kink, broken filars on a shocking coil and other irregularities) the following chest x-rays or other available imaging studies will be collected (if available): a) earliest imaging study showing evidence of externalized conductors or other visual lead anomaly and b) latest imaging study that does not show any evidence of externalized conductors or other visual lead anomaly

Data will be collected at 6, 12, 18, 24, 30, and 36 months post enrollment and during any unscheduled follow-up visits due to patient symptoms suggestive of or with evidence of lead electrical problems. Additionally, cinefluoroscopy (AP, LAO 45° or the best possible LAO view, RAO 45° or the best possible RAO view) will be performed in all patients to determine the incidence and mechanical progression of externalized conductors at the 12, 24, and 36 month visits.

During any follow-up visits, device data and stored electrograms will be collected. All clinical events such as hospitalizations, emergency room visits, and adverse events will also be collected. All study data, including device data and stored electrograms will be sent to SJM electronically. If any lead being followed in this study develops a significant electrical abnormality suggestive of lead malfunction and x-ray or cinefluoroscopy would be performed as per the site standard of care then copies of x-ray or cinefluoroscopy should be submitted to SJM.

During the course of the study, any explanted leads should be returned to Returned Goods, St Jude Medical, Sylmar, CA, for analysis.

Study Flow Diagram

